### Exclusion criteria:

- Patients deemed to have poor prognosis, or patients to receive palliative treatment only (as advised by the Clinical Oncology team).
- Patients with less than 6 teeth before the radiotherapy start date.
- Patients with recurrent head and neck cancer, or patients receiving a repeat course of head and neck radiotherapy.
- Patients with diseases affecting tooth development (e.g. amelogenesis or dentinogenesis imperfecta) or salivary gland function (e.g. Sjogren's Syndrome).
- Patients with pre-existing trismus (mouth opening less than 35mm).

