### Denture hygiene instruction

- Don't wear dentures during the course of radiotherapy if possible
- Rinse dentures after every meal in cold running water
- Clean dentures at least once daily with a toothbrush and 5,000 ppm Duraphat fluoride toothpaste
- Soak in Milton's (1 in 80 dilution) overnight if the denture is made of plastic only
- Alternatively, soak in Corsodyl (chlorhexidine gluconate) 0.2% overnight if the denture has metal components

A dental treatment plan will be formulated for each patient to ensure adequate dental fitness prior to radiotherapy. Consultants in Restorative Dentistry, will oversee patients' treatment plans. Dental treatment required pre-radiotherapy (e.g. restorations and extractions) will be co-ordinated by the School of Dentistry in line with current practice, including the possibility of routine treatment within the primary care setting (i.e. completed by the patient's general dental practitioner).

To facilitate the micro-costings study, all patients will be asked to retain details of any treatment costs that they incurred from their general dental practice. Patients will be asked to provide this cost information at follow-up appointments (for example, with the production of invoices). Information on the cost of dental treatment incurred will be recorded on each patient's anonymised questionnaire booklet completed at the subsequent follow-up appointment.

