## **Statistical analysis**

Primary outcome measures to be analysed include: (1) the number of carious teeth and (2) the presence of periodontal disease.

(1) Initial comparisons between the radiation dose to the 'spared' parotid gland and the number of carious teeth will be performed using independent t-tests (categorising radiation dose as <20Gy and >20Gy) and ANOVA (categorising radiation dose as <20Gy, 20-30Gy, 30-40Gy, and >40Gy) as appropriate. Adjusted analysis will be performed using multiple linear regression, with the number of carious teeth as the outcome variable, radiation dose to the 'spared' parotid gland as an explanatory variable

(categorised as above) along with potential confounding variables: dental radiation dose, oral hygiene practice, diet, and mouth opening. Without categorising radiation dose, a separate analysis will be conducted using linear regression with the number of carious teeth as the outcome variable and radiation dose to the 'spared' parotid gland (Gy) as the explanatory variable to give the increase in the number of carious teeth per 10 unit increase in Gray. If the number of carious teeth is not normally distributed transformations will be used prior to analysis or equivalent non-parametric techniques will be used.

(2) Initial comparisons of the association between radiation dose to the 'spared' parotid gland (categorised as above) and the presence of periodontal disease (Yes/No) will be performed using chi-square tests. Adjusted analysis will be performed using logistic regression with presence of periodontal disease as the outcome variable, radiation dose to the 'spared' parotid gland as the explanatory variable and dental radiation dose, oral hygiene practice, diet, smoking, medical history, and mouth opening as potential confounders.

Similar analyses will be undertaken to determine the effects of dental radiation dose and tumour location on the number of carious teeth and the presence of periodontal disease in post-radiotherapy head and neck cancer patients.

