Secondary outcomes to be analysed include: quality of life, salivary flow rate, diet, oral hygiene practice, mouth opening, xerostomia (all change from baseline); tooth loss, and denture wear. Dichotomous outcomes will be analysed using chi-square tests and logistic regression as above. Continuous outcomes will be analysed as above, apart from variables with baseline measurements, for which ANCOVA will be used to compare outcome measurements adjusting for baseline. Adjusted analyses will use multiple linear regression models as above but with baseline measurements as an additional explanatory variable.

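### Denture wear, a secondary outcome, is analysed without baseline denture status, so wear that predates radiotherapy is mixed with wear that follows it

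*Combined protocol and SAP*

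**What the plan says.** All references are to the combined protocol and SAP.

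- **Outcome list (Statistical analysis).** Quality of life, salivary flow, diet, oral hygiene, mouth opening and xerostomia are analysed relative to baseline. Two outcomes follow that bracket: "mouth opening, xerostomia (all change from baseline); tooth loss, and denture wear".
- **Analysis route (Statistical analysis).** "Dichotomous outcomes will be analysed using chi-square tests and logistic regression as above". The logistic model this points back to, the one for periodontal disease, lists "dental radiation dose, oral hygiene practice, diet, smoking, medical history, and mouth opening as potential confounders". Neither denture status nor a baseline value of the outcome is among them.
- **Where baseline adjustment applies (Statistical analysis).** It is offered first for continuous variables: "Continuous outcomes will be analysed as above, apart from variables with baseline measurements, for which ANCOVA will be used". It is then extended to the adjusted models: "Adjusted analyses will use multiple linear regression models as above but with baseline measurements as an additional explanatory variable". Both sentences concern continuous outcomes or linear models.
- **Who is in the cohort.** The only tooth-count exclusion is "Patients with less than 6 teeth before the radiotherapy start date". Denture wearers are not excluded. The pre-radiotherapy advice has its own section on dentures (Denture hygiene instruction), which includes "Don't wear dentures during the course of radiotherapy if possible".

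The documents do not say whether denture wear means current wear or new wear, or at which visit it is judged.

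**The concern.** Denture wear is a state that may already be present when a patient enters the study. The reason to analyse it against radiation dose is to learn whether dose is followed by patients coming to need dentures. An analysis that ignores entry status cannot separate those patients from the ones who arrived with dentures.

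Dose is not randomised: radiotherapy is planned individually (Radiation dose and tumour location determination). There is therefore no design reason for existing denture wear to be balanced across dose groups. The plan adjusts other secondary outcomes for their baseline value, so this is a gap in its own approach. At stake is whether the denture-wear result can be read as something that follows radiotherapy. No primary result is at stake.

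**Working it through.** **The plan's own figure.** There is none for denture wear. The Sample size section concerns carious teeth only: 150 evaluable patients and an 80%/20% split around 20 Gy. I take only the group sizes from it: 0.20 × 150 = 30 under 20 Gy and 0.80 × 150 = 120 over 20 Gy.

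**Assumed inputs.** Let *b* be the proportion wearing dentures at baseline, with those patients still wearing them at follow-up. Let *p* be the proportion of baseline non-wearers who become wearers. Subscript 0 is under 20 Gy and subscript 1 is over 20 Gy. The documents give no value for either, so ranges are shown.

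**Step 1: equal baseline wear.** Follow-up prevalence is q = b + (1 − b)p, so q₁ − q₀ = (1 − b)(p₁ − p₀). The odds ratio is [q₁/(1 − q₁)] / [q₀/(1 − q₀)]. With p₀ = 10% and p₁ = 25%:

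| b | q₀ | q₁ | Difference (points) | Odds ratio |
|---|---|---|---|---|
| 0% | 10% | 25% | 15 | 3.00 |
| 20% | 28% | 40% | 12 | 1.71 |
| 40% | 46% | 55% | 9 | 1.43 |
| 50% | 55% | 62.5% | 7.5 | 1.36 |

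For b = 20%: q₀ = 0.20 + 0.80 × 0.10 = 0.28 and q₁ = 0.20 + 0.80 × 0.25 = 0.40. The odds ratio is (0.40/0.60)/(0.28/0.72) = 1.71.

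**Step 2: unequal baseline wear.** Now q₀ = b₀ + (1 − b₀)p₀ and q₁ = b₁ + (1 − b₁)p₁.

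| New wear p₀ / p₁ | Baseline wear b₀ / b₁ | q₀ / q₁ | Odds ratio | Odds ratio for new wear |
|---|---|---|---|---|
| 10% / 30% | 10% / 30% | 19% / 51% | 4.44 | 3.86 |
| 10% / 30% | 30% / 10% | 37% / 37% | 1.00 | 3.86 |
| 10% / 30% | 40% / 10% | 46% / 37% | 0.69 | 3.86 |
| 20% / 20% | 10% / 30% | 28% / 44% | 2.02 | 1.00 |
| 20% / 20% | 30% / 10% | 44% / 28% | 0.49 | 1.00 |

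So the association can be inflated, hidden, reversed, or created where there is none.

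**Step 3: does restricting to baseline non-wearers cost power?** Take p₀ = 10%, p₁ = 30% and equal b, with a two-sided 5% test and the normal approximation.

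- *All patients, b = 20%.* Groups of 30 and 120, with 28% v 44%. The pooled proportion is (30 × 0.28 + 120 × 0.44)/150 = 0.408. The null SE is √[0.408 × 0.592 × (1/30 + 1/120)] = 0.1003. The alternative SE is √(0.28 × 0.72/30 + 0.44 × 0.56/120) = 0.0937. Power is Φ[(0.16 − 1.96 × 0.1003)/0.0937] = Φ(−0.39) = 35%.
- *Baseline non-wearers only, b = 20%.* Groups of 24 and 96, with 10% v 30%. The pooled proportion is 0.26, the null SE 0.1001 and the alternative SE 0.0771. Power is Φ[(0.20 − 1.96 × 0.1001)/0.0771] = Φ(0.05) = 52%.
- The same comparison gives 46% v 58% at b = 10%, and 22% v 38% at b = 40%.

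Under these assumptions the smaller sample is more than repaid by the larger contrast.

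**The case against.** Several points on the other side have force.

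- **The outcome is undefined.** A reader might take it as stated that the plan analyses a yes/no at follow-up. It is not stated. Denture wear is paired with tooth loss, which is naturally an event since baseline, so the sponsor may have meant new wear. This stands as a limit on the reading. It does not rescue the text, which nowhere restricts the outcome to new wear.
- **Existing wearers need not stay wearers.** A reader might infer that they are events from the start whatever their dose. The documents do not support that. Patients are advised against denture wear during radiotherapy where possible, extractions change the mouth before and after treatment, and some may stop wearing a denture. Persistence is therefore an assumption of the working.
- **Two different quantities are compared.** Under the working's assumptions, 12 points is the correct difference in denture prevalence for the whole cohort, and 15 points applies to baseline non-wearers. This is true. The whole-cohort figure is a legitimate description, but it does not isolate what happens after radiotherapy.
- **How many wear dentures at entry is unknown.** The denture advice shows that some are expected but gives no frequency. The mention of prosthetic incisors under mouth opening could refer to fixed prostheses or implants, so it is not relied on here. If few patients wear dentures at entry, the effect is small.
- **The data may already be collected.** A reader might infer that denture status is not recorded. The assessment sections do not name it, but the items of the cited form and questionnaire are not shown, so this cannot be judged.

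**Conclusion.** The point holds as a gap in the analysis of one low-priority secondary outcome. The written route uses no baseline denture status, the baseline-adjustment sentences do not reach a dichotomous outcome, and existing wearers are eligible.

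It would be tempting to conclude that the plan biases a dose effect towards the null. That goes too far. Pure dilution, by the factor (1 − b), needs baseline wear to be both unrelated to dose and persistent. In a non-randomised comparison the first condition cannot be assumed, and the error can go either way: the illustrations run from an odds ratio of 0.69 to 4.44 where the value for new wear is 3.86, and from 0.49 to 2.02 where it is 1.00. The size in this study is unknown, because every denture-wear rate used is an assumption.

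The clinical hypothesis and the sample size calculation do not mention denture wear. The primary analyses, the 150 evaluable patients and the 215 to be recruited are unaffected. Even after correction, power for this outcome would be modest in the scenarios shown (38% to 58%), so the gain is mainly in interpretation.

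**What to change.** In the secondary-outcome paragraph of Statistical analysis:

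1. Define the analysed outcome as new denture wear after radiotherapy among patients not wearing a denture at baseline, and name the visit at which it is judged. Alternatively, keep all patients and add baseline denture status to the logistic model as a covariate or stratum. The restricted analysis is preferable if nearly all baseline wearers remain wearers, because the baseline term would then produce separation in the logistic fit.
2. State that dentures made necessary by the pre-radiotherapy dental-fitness extractions count as baseline status, not as new wear. The baseline assessment precedes those extractions, so without this rule such dentures would be attributed to the period after radiotherapy.
3. Confirm that the existing assessment form or questionnaire records denture status at all four visits, and add a yes/no item if it does not.

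The cost is a few sentences, possibly one data field per visit, and a smaller analysed sample if the restricted definition is chosen.

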## **Micro-costings analysis**

A micro-costings analysis will be undertaken to evaluate patient and healthcare costs in relation to the diagnosis and treatment of pre- and post-radiotherapy dental disease.

-Patient costs to be evaluated include: total cost of travel to dental appointments, total time off work to attend for dental treatment, total cost of dental treatment incurred pre and post-radiotherapy (general or private practice), total out-of-pocket expenses (e.g. pain-relief medications). Patients will also be asked to state their gross annual income in order to be able to quantify their individual economic burden of dental disease.

-Healthcare costs to be evaluated include:

(1) clinical and administration hospital costs for pre- and post-radiotherapy dental assessments and treatment via the National Schedule of Reference Costs for NHS Trusts.

(2) remuneration of primary care dental practitioners via the Statement of Dental Remuneration made available by the Business Services Organisation.

Cost savings due to improved treatment planning of patients will also be hypothesised.

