Patients will be asked to refrain from smoking, eating and drinking, and other forms of oral stimulation (e.g. oral hygiene) 90 minutes prior to the collection of saliva. It is anticipated that the length of each patient's pre-radiotherapy dental assessment will be at least 90 minutes (based on current clinical practice). Patients will therefore be instructed not to engage in oral stimulation for 90 minutes after they have signed the written consent form at the start of the appointment.

-Ruler measurement of **mouth opening**. Maximum interincisal distance will be measured when the upper and lower central incisors are present (natural or prosthetic). Alternatively, the alveolar ridge(s) will be used as a reference point for measurement where no natural or prosthetic central incisors are present.

All of the above data, including the Oral Health Assessment Forms, will be recorded and stored in patients' clinical records (dental notes).

**-Oral hygiene practice and dietary assessments** will be performed using the World Health Organization's Oral Health Questionnaire for Adults.

**-Quality of life** and experience of **xerostomia** will be assessed using questionnaire booklets containing the European Organization for Research and Treatment of Cancer (EORTC) QLQC30 quality-of-life instrument, the associated head and neck specific module HN35, the Oral Health Impact Profile, and the modified Xerostomia Questionnaire.

**-Micro-costings study.** Patients will also be asked to complete a short questionnaire enquiring of their gross annual income, the mode of transport they used for attending their dental appointment, and whether another person accompanied them to their dental appointment. The micro-costings study questionnaire will be attached to the oral hygiene/diet/quality of life/xerostomia questionnaire booklet outlined above.

The questionnaire booklets will be completed anonymously. Upon acceptance into the study, a random number generator will assign each recruited patient a 6-digit anonymous code. Each patient will be informed of his or her anonymous code. This will be the only identifier recorded on completed questionnaire booklets.

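### The micro-costings analysis plans totals for time off work and out-of-pocket spending, but no data source is described for either, and travel cost is only partly covered

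*Combined protocol and SAP*

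**What the plan says.** The Micro-costings analysis section of the combined protocol and SAP names four patient costs:

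- what patients spend on travelling to their dental visits;
- lost working time, given as "total time off work to attend for dental treatment";
- charges paid to dental practices before and after radiotherapy;
- incidental spending, given as "total out-of-pocket expenses (e.g. pain-relief medications").

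It adds that income will be requested so that each patient's economic burden can be quantified.

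Two collection routes are described for patient costs. Under Clinical assessment, the micro-costings item is a brief set of questions, described as "enquiring of their gross annual income, the mode of transport they used for attending their dental appointment, and whether another person accompanied them". In the text after the Denture hygiene instruction, "all patients will be asked to retain details of any treatment costs that they incurred from their general dental practice". These charges are reported at follow-up and entered on the questionnaire booklet.

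**The concern.** Each patient cost is planned as a total, so each needs a recorded quantity, such as hours or days, money spent, or distance or fare. The questionnaire as described does not ask for time off work or for purchases, and its travel items do not include a quantity that can be priced directly.

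If the study ran as written, two components of the patient's economic burden would be empty and a third would rest on assumptions that the plan does not state. The burden would then be understated, or filled in afterwards by methods chosen once the data were in. Hours missed and small purchases leave little trace in clinical records, so if nobody asks at the visits, they cannot be reliably recovered later.

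**Working it through.** The plan gives no figure to reproduce and no arithmetic applies beyond a count. The check sets each planned patient cost against every collection route described.

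**Routes considered**

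1. Clinical assessment, micro-costings questionnaire: income, transport mode, companion.
2. Text after Denture hygiene instruction: charges from general dental practice, reported at follow-up, for example with invoices.
3. Protocol for post radiotherapy dental assessments: repeats the micro-costings study at 6, 12 and 24 months with the same methods, and names no new cost items.
4. Other special investigations (post-radiotherapy): general dental practitioners report treatment they carry out. This gives treatment events, not patient time or spending.
5. Spreadsheets: questionnaire results are entered, with no further cost items named.

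**Coverage**

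| Planned patient cost | Described source | Status |
|---|---|---|
| Dental treatment charges | Route 2 | Covered |
| Time off work | None; income could put a value on lost time, but the amount of time is not collected | No source |
| Out-of-pocket expenses | None; route 2 is confined to practice treatment charges and does not reach items such as pain relief | No source |
| Travel | Route 1: mode and companion, without distance, fare or parking | Partial |

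The count is 2 with no source + 1 partial + 1 covered = 4 planned components.

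**Travel in more detail.** The analysis wants a total over appointments, while the questionnaire asks how the patient came to the one being attended ("enquiring of their gross annual income, the mode of transport they used for attending their dental appointment"). Both the pre- and post-radiotherapy treatment-planning text allow routine treatment in primary care, so some dental trips will be to general practices. Nothing described clearly counts those trips or records how they were made.

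**Recall.** The follow-up visits are 6 months apart (12 − 6) and then 12 months apart (24 − 12). The first is timed from radiotherapy, so the gap from baseline to that visit is longer than 6 months. Details not asked for at one visit would have to be remembered over a longer span at the next.

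**The case against.** The strongest reply is that the questionnaire form is not in the documents and the description of it is one sentence. That sentence is demonstrably not a full account of the booklet's cost content, because treatment charges are also to be entered on the booklet and it does not mention them. The Micro-costings analysis section, after listing the costs, says that patients will additionally be asked for income, which can be read as implying that they are asked about the listed costs too. A reader might infer that the form lacks these items, or that the costs cannot be computed. The documents do not support either statement. They support only the finding that no collection is described.

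Travel also deserves a fairer reading. Transport mode and companion are direct inputs to a travel cost, the study visits have a fixed destination (the School of Dentistry, Belfast), and the code list links each booklet to hospital record numbers. With an assumed or record-derived distance and a unit cost per mode, travel to study visits could be estimated. The plan does not state that method, and it would not clearly reach trips to general practices.

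Nor is it right to infer that treatment cost is the only patient-cost information collected, since income, mode and companion are collected as well.

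These points limit how the finding may be worded. They do not supply a source for time off work or out-of-pocket spending. The possible reading of the income sentence names no instrument, question or time point.

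**Conclusion.** The concern holds in a limited form. Two of the four planned patient costs have no described data source. A third, travel, has transport mode and companion but no distance, fare or parking, no stated costing method, and no clear coverage of trips to general dental practices. The fourth has a described source.

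The conclusion assumes that the sections listed above are the full description of patient-cost collection. It would become a documentation error alone if the form already contains the missing items.

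A reader might infer that the whole economic analysis fails. It does not. The healthcare-cost part has its own named sources, and the micro-costings are not among the primary or listed secondary outcomes, so the dose–caries and dose–periodontal analyses do not depend on them. The effect is confined to the patient-cost part, where it is more than a missing detail because the data cannot be reliably rebuilt later.

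**What to change.** Add these items to the existing booklet at each visit, covering the period since the last visit (at baseline, the pre-radiotherapy dental care to date):

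- the patient's time off work for dental treatment;
- out-of-pocket dental spending;
- the number of dental trips, including those to general dental practices, with distance or fare.

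State in the Micro-costings analysis section how transport mode and distance or fare become a travel cost. The companion's lost work time is not among the listed patient costs and need not be added.

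If the form already contains these items, correct its description under Clinical assessment. If they will not be collected, remove or qualify the corresponding components in the Micro-costings analysis section.

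The cost is a short amendment and slightly more patient burden at each visit. Answers will rest on recall over roughly 6 to 12 months, which the report should acknowledge as a limitation.
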